## Data Input Procedure

Data collection will be using the secure REDcap system. All data will be handled in accordance with the Data Protection Act 1998 and GDPR 2018. Each local lead will be provided with a unique username and password and collected prospectively for maximum accuracy. Completed datasheets will be entered into the secure REDcap system REDcap will be hosted by the University of Swansea.

REDcap accounts will not be issued until evidence is provided via hospital local leads that the following approvals are in place at each centre:

- i. Successful registration of ELF at the hospital site
- ii. Caldicott Guardian permission for data to be submitted to REDcap

## **Training Materials:**

As with previous multicentre studies, we will deliver online training to ensure standardisation. This will be delivered through online presentation of the project rationale, how to complete the pro forma, and how to use the REDcap system for data entry.

## Validation

Validation will be performed on 25% of data fields for 10% of cases. The validated fields will include key demographic and outcome data.

## Data analysis

Statistical support will be provided by the study statistician ([name]) throughout the project.

Description of demographics of included patients including their demographics (gender, age), baseline clinical characteristics (frailty score, NELA score, comorbidities and polypharmacy). Complications and outcomes (Clavien-Dindo, discharge destination, 30 and 90-day mortality) will also be described. Missing/incomplete data will be presented and explored.

The Primary outcome to estimate the NoLAP proportion will be carried out with an asymptotic method, and presented with a 95% confidence interval.

The primary outcome to estimate the difference in 90-Day mortality between those with a NOLAP and ELAP will be carried out with a multi-level logistic regression, fitting patients within hospitals as a random site effects. The model will be adjusted for pre-operative patient: age; sex; and frailty status.

A full Statistical analysis plan will be reported prior to the data lock, and will be largely described in the published protocol.

Following analysis, each unit will be offered to receive their own raw data, and a summary of national data. This will allow comparison to local performance and enable local quality improvement work.

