# STUDY SYNOPSIS

Title of Study:	Defining the Denominator: Emergency Laparotomy and Frailty Study 2.	
Study Centre:	Multicentre	
Duration of Study:	25 months	
Primary Objective:	Identify a U.K. consecutive series of older adults presenting with acute abdominal pathology potentially treatable by emergency laparotomy where the decision is made not to undergo surgery (NoLAP) and their associated 90- day mortality.	
Secondary Objective:	Collect, define and characterise the reasoning behind the NOLAP decision.	
Primary Endpoint:	Characterise NoLAP patient populations and document 90-day mortality.	
Rationale:	Older patients that require, but do not undergo emergency laparotomy (NoLAP) are an undefined and uncharacterised population. In contrast to those older adults that undergo emergency surgery, it is not known how many patients constitute this NoLAP group, what characteristics they have, what the reasons are for not undergoing surgery and what their short-term outcomes are.	
Methodology:	Prospective cohort study	
Sample Size:	700	
Screening:	n/a	
Registration/ Randomisation:	Via REDCap database.	
Main Inclusion Criteria:	
 
65 years or older
 
requires emergency laparotomy for pathology consistent with inclusion into NELA
 
does not undergo emergency laparotomy
 
had review by trained surgeon
 
	
Main Exclusion Criteria:	
 
under 65 years of age
 
no surgical review
 
failed conservative management
 
	
Product, Dose, Modes of Administration:	N/A	
Duration of Treatment:	N/A	
Statistical Analysis:	Detailed later.	

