There are only two published works that have reported on the NoLap population. The Perth (Australia) Emergency Laparotomy Audit prospectively collected NoLAP numbers as part of analysing ELAP patients and found them to account for only 6% of the overall population being considered for emergency laparotomy [7]. However, this small number limits characterisation of NoLAP patients and more importantly, comparison to ELAP patients. The second study prospectively recorded over three hundred patients requiring ELAP for over 14 months [8]. Patients were included according to the NELA criteria with both groups having the same data recorded. In addition, the casenotes were reviewed to ascertain the reason for the NoLAP decision. This study found NoLAPs accounted for a third of all patients (32%) requiring an ELAP with a third of these being alive at 30 days with normal admission creatinine and lactate levels increasing the likelihood of survival. This is the first work that has attempted to characterise the U.K. NoLAP population, but is limited by being both single centred and by providing limited information on the decision behind NoLAP.

We aim to apply the findings and challenges from this work into the design of this multi-centred cohort study, to definitively define the denominator.

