## Patient numbers and power calculation

ELF Study recruited 957 patients from 49 sites and had a mortality of 20% at 90-days, similar to NELA findings (17-25% with increasing age). For aim 1: From previous work it is estimated that the proportion of patients to experience an NoLAP is approximately 32%. We will estimate this proportion with a 95% within +/- 3.75% by following up 590 patients, and assuming a small loss to follow up rate of 10%, we will recruit 700 patients.

With 25 000 ELAPs recorded every year in England and Wales, 32% of NoLAPs gives an estimate of 8000 NOLAPS per year. For a 3-month recruitment window we predict that the recruitment pool is 2000 making the study target of 700 achievable.

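### The primary NoLAP proportion is sized as if patients were independent, and no allowance for hospital clustering is stated for its 95% interval; an unadjusted interval is too narrow for any positive ICC

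*Protocol*

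**What the plan says.** The protocol's Data analysis section names two primary analyses. For the NoLAP proportion it says: "The Primary outcome to estimate the NoLAP proportion will be carried out with an asymptotic method, and presented with a 95% confidence interval". Clustering is not mentioned. For the difference in 90-day mortality between NoLAP and ELAP patients, the next paragraph says the analysis "will be carried out with a multi-level logistic regression, fitting patients within hospitals as a random site effects".

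The section on patient numbers and power takes an expected proportion of 32% from earlier work and says: "We will estimate this proportion with a 95% within +/- 3.75% by following up 590 patients". It continues: "assuming a small loss to follow up rate of 10%, we will recruit 700 patients". It gives no ICC, cluster size, design effect or expected number of sites. The only site count there is 49, which belongs to the earlier ELF study.

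The Data analysis section also promises a full statistical analysis plan before data lock.

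**The concern.** Whether a patient becomes a NoLAP is decided by the local team, so patients in one hospital are likely to resemble each other on this outcome more than patients in different hospitals do. The protocol accepts this for mortality. For the proportion, it states a precision that assumes independence and a method with no provision for clustering.

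If the text is followed at face value, the interval around the study's main descriptive figure will be too narrow. The study sets out to establish that denominator for the UK, so readers will rely on the interval. On one reading of the sample size, the promised precision would also be missed.

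**Working it through.** **Inputs from the protocol.** p = 0.32, half-width h = 0.0375, 95% confidence, 590 followed up, 700 recruited, 10% loss (all from Patient numbers and power calculation).

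**Assumptions.** 49 equal-sized sites, borrowed from ELF, and an ICC of 0.005 to 0.10. The protocol gives neither for this study.

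**Step 1: reproduce the plan's figure.** For independent patients, n = 1.96² × p(1−p) / h² = 1.96² × 0.32 × 0.68 / 0.0375² = 594. At n = 590 the half-width is 1.96 × √(0.32 × 0.68 / 590) = 3.76 points (Wald), or 3.75 (Wilson). The plan's figures are recovered with no design effect.

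**Step 2: allow for clustering, 590 candidates.** Mean cluster size m = 590/49 = 12.0. Design effect DE = 1 + (m−1) × ICC. True half-width = 3.76 × √DE. Coverage of the unadjusted interval = 2Φ(1.96/√DE) − 1. The n needed is 594.4 × DE.

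| ICC | DE | Half-width (points) | Coverage of unadjusted 95% CI | n needed for 3.75 points |
|---|---|---|---|---|
| 0.005 | 1.055 | 3.87 | 94.4% | 628 |
| 0.01 | 1.11 | 3.97 | 93.7% | 661 |
| 0.02 | 1.22 | 4.16 | 92.4% | 726 |
| 0.05 | 1.55 | 4.69 | 88.4% | 923 |
| 0.10 | 2.10 | 5.46 | 82.3% | 1,251 |

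**Step 3: slack in the 700.** After 10% loss, 700 × 0.9 = 630 remain. Then 3.75 points survives a DE of 630/594.4 = 1.06, which is an ICC of about 0.005 (m = 12.9). If all 700 count, it survives a DE of 700/594.4 = 1.18, an ICC of about 0.013 (m = 14.3). With all 700, the half-width is 3.89 points at ICC 0.02 and 4.46 at 0.05.

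**Step 4: the other reading, 700 NoLAP patients.** The candidates then number 700/0.32 = 2,188, and the unadjusted half-width is 1.96 × √(0.32 × 0.68 / 2,188) = 1.95 points. With 49 sites, m = 44.6.

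| ICC | DE | Half-width (points) | Coverage of unadjusted 95% CI |
|---|---|---|---|
| 0.01 | 1.44 | 2.34 | 89.8% |
| 0.02 | 1.87 | 2.68 | 84.8% |
| 0.05 | 3.18 | 3.49 | 72.8% |
| 0.10 | 5.36 | 4.53 | 60.3% |

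Here 3.75 points holds while DE ≤ (3.75/1.955)² = 3.68, so up to an ICC of (3.68 − 1)/43.6 ≈ 0.06. Coverage is worse than in step 2 because the clusters are larger.

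**The case against.** **The method is not literally a simple binomial.** A cluster-robust variance is also asymptotic, so the wording does not exclude the fix, and the analysis plan could still specify it. That stands as a point about wording. But the sizing has no design effect, and the paragraph that follows names a multilevel model for mortality, so the unadjusted reading is the natural one. A later plan can choose the variance, but the precision already claimed in the protocol would still need restating.

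**The promised precision may be met.** A reader might infer that 3.75 points will be missed. The documents do not support that without qualification. The synopsis gives a sample of 700 with inclusion criteria that describe NoLAP patients, and the recruitment pool of 2,000 is also NoLAPs. On that reading 3.75 points is met up to an ICC of about 0.06. On the other reading the slack in the 700 absorbs a small ICC. Since NoLAP status is known at the decision, loss to follow-up need not shrink this denominator.

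**The ICC is unknown and could be small.** This stands. At 0.005 to 0.01 with 590 candidates, coverage is still about 94%.

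**The Background might seem to show a large ICC.** One cited audit "found them to account for only 6% of the overall population being considered for emergency laparotomy", and the other study reports 32%. A reader might take this gap as evidence of strong variation between hospitals. The first is Australian and the second a single UK centre, so country and setting are confounded with site. The gap gives no estimate of an ICC among UK hospitals and is not used here.

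**Uneven case finding is a bias problem.** Each site devises its own way of identifying NoLAPs. Cases missed this way lower the estimate itself, and no variance adjustment corrects that. This stands as a limit on what the fix achieves.

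**Conclusion.** The point holds for the interval on both readings of the sample size: for any positive ICC, an interval that ignores hospitals is too narrow. It is more than a detail left for later, because the protocol already states a method and a precision, and it recognises clustering in its other primary analysis.

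The size is conditional on 49 equal sites and an assumed ICC; unequal sites would generally make it worse. With 590 candidates the loss runs from trivial (about 94% coverage at ICC 0.005 to 0.01) to serious (about 82% at 0.10). With about 2,188 candidates it is larger: about 90%, 85% and 73% at ICC 0.01, 0.02 and 0.05.

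That the 3.75 points will be missed is a narrower conclusion. It holds only if the 590 or 700 are all candidates for laparotomy and the ICC exceeds the small slack in step 3.

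**What to change.** In Data analysis, state that the NoLAP proportion will be estimated with a cluster-robust variance by hospital, or as the marginal proportion from a random-intercept logistic model with hospital as the random effect. Report the between-site variation with it.

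In Patient numbers and power calculation, say whether 590 and 700 count all candidates or NoLAP patients only. Then give the expected number of sites and restate the precision with a design effect over a stated ICC range, for example 0.01 to 0.10.

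The cost is a few sentences and a small change to the analysis code. No new data are needed, and the stated precision becomes somewhat less favourable. Bias from NoLAPs missed by uneven case finding has to be addressed separately.

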## Aims

This study aims to:

1) Identify a U.K. consecutive series of older adults presenting with acute abdominal pathology potentially treatable by emergency laparotomy where the decision is made not to undergo surgery (NoLAP) and their associated 90-day mortality.

2) Collect, define and characterise the reasoning behind the NOLAP decision.

3) Define potential prognostic markers for mortality that could aid decision-making in the future (including frailty, NELA score and sarcopenia).

4) Compare aims 1 and 3 to those that underwent surgery (ELAP) during the same time frame as the NoLAP population.

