#### Variables collected

The following clinical parameters will be collected for NOLAP population: age; sex; place of residence (home with no carers, home with carers, intermediate care, residential home, nursing home); ASA (American Society of Anaesthesiologists); surgical diagnosis (pre-operatively); NELA score; Clinical Frailty Score (Rockwood, 1 to 7); co-morbidities (Charlson; total number of co-morbidities); polypharmacy (5+ medications: yes/no) CT performed within 48 hours of decision (yes/ no); CT

diagnosis; date of assessment for laparotomy, time of day and location (most relevant according to the following list: general surgical ward; other surgical ward; orthopaedics; gynaecology; geriatrics; acute medical ward; other medical ward). Preoperative (within 8 hours of surgical decision) blood markers will also be recorded: lactate; C reactive protein; creatinine and WCC. The actual procedure performed will be recorded for the ELAP patients only.

For comparison to ELAP. This data will be retrieved directly from NELA and ELLSA databases with no extra data required by each participating site.

Remaining variables: length of hospital stay; length of critical care stay (ICU and HDU combined). Both groups will then be followed up for: 30-day complications (Clavien-Dindo Grading); date of discharge; discharge destination (home with no carers, home with carers, intermediate care; residential home, nursing home); 30-day and 90-day mortality and death at 1 year. Actual date of death and cause of death (1a on death certificate) will be recorded.

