# Appendix A. Decision-making Options for NoLAP.

Must select at least one of these factors as the MAIN influencing factor.

Patient Factors	Yes/	Surgical Factors	Yes/
	No		No
Patient does not wish to have surgery (Drop down menu of reasons if selecting 'yes': chronic pain, management of stoma, does not want to lose independence i.e. institutionalisation, other – free text)		Poor Pre-op Fitness (Drop-down menu options if selecting 'yes': home oxygen; nursing home resident; bed bound; housebound; advanced comorbidity; other – free text)	
Has Living will in place		Poor prognostic pathology (Drop-down menu options if selecting 'yes': global ischaemia, advanced malignancy; other –free text)	
Patient involved in decision (Drop-down options if selecting 'no': Reduced GCS; severe dementia; acute delirium; power of attorney in place; other – free text)		
 
High prognostic score
 
(Drop-down menu options if selecting 'yes': high NELA score; high frailty score; high P-Possum score, high SORT score)
 
If frailty score used: define which score
 
If yes selected for any score, record actual value (frailty score value or predicted mortality value)
 
	
Anyone else representing the patient involved in the decision (Drop down options if selecting 'yes': next of kin, legal guardian, friend, other)		Surgeon involved in decision (Drop-down menu if selecting 'yes': consultant, associate specialist, staff grade, registrar, core trainee)	

Anaesthetic Factors	Yes/	Intensive Care Factors	Yes/
	No		No
Poor Pre-op Fitness		Poor Pre-op Fitness	
(Drop-down menu options: home oxygen; nursing home resident; bed bound; housebound; advanced comorbidity; other – free text)		(Drop-down menu options: home oxygen; nursing home resident; bed bound; housebound; advanced comorbidity; other – free text)	
Poor prognostic pathology		Poor prognostic pathology	
(Drop-down menu options: global		(Drop-down menu options: global ischaemia,	

ischaemia, advanced malignancy; other –		advanced malignancy; other -free text)	
free text)			
,			
High prognostic score		High prognostic score	
(Drop down many options if colocting was'		(Drop down many options if colocting (yes), high	
(Drop-down menu options if selecting 'yes':		(Drop-down menu options if selecting 'yes': high	
high NELA score; high frailty score; high P-		NELA score; high P-Possum score; high SORT score;	
Possum score; high SORT score)		high frailty score)	

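### The NoLAP versus ELAP mortality model adjusts only for age, sex and frailty, omitting NELA score, diagnosis and comorbidity, which the Protocol lists as reasons for not operating

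*Protocol*

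**What the plan says.** The Data analysis section of the Protocol sets out the comparison: "The primary outcome to estimate the difference in 90-Day mortality between those with a NOLAP and ELAP will be carried out with a multi-level logistic" model, with patients nested in hospitals through a random site effect. It then closes the covariate list: "The model will be adjusted for pre-operative patient: age; sex; and frailty status". NELA score and comorbidities appear in that section only among the characteristics to be described.

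The Variables collected section lists much more for NoLAP patients, including "surgical diagnosis (pre-operatively); NELA score; Clinical Frailty Score (Rockwood, 1 to 7"), ASA grade and Charlson comorbidity. It adds that "blood markers will also be recorded: lactate; C reactive protein; creatinine and WCC", within 8 hours of the surgical decision. Data for the ELAP comparison are to come from the NELA and ELLSA databases, with nothing extra asked of sites.

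Appendix A records why surgery was not done. Under surgical, anaesthetic and intensive care factors it offers "Poor prognostic pathology" (with global ischaemia and advanced malignancy as options), a high prognostic score (NELA, P-Possum, SORT or frailty) and poor pre-operative fitness (with advanced comorbidity as an option).

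On the outcome side, aim 3 is to "Define potential prognostic markers for mortality that could aid decision-making in the future (including frailty, NELA score and sarcopenia"). The Background reports, from the earlier single-centre UK study of NoLAP patients, "normal admission creatinine and lactate levels increasing the likelihood of survival".

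**The concern.** The two groups are formed by a clinical decision. A variable that influences the decision and also predicts death will distort the comparison unless it is adjusted for. Of the three covariates in the model, only frailty corresponds to a reason for not operating listed in Appendix A. Age and sex do not stand in for the acute pathology, the predicted operative risk or the burden of comorbidity.

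An odds ratio described as adjusted will be read as corrected for case mix. With this covariate set, part of it is likely to reflect sicker patients and less survivable pathology in the NoLAP group. The Protocol names no sensitivity analysis for this comparison and carries no caveat about confounding.

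**Working it through.** **1. Each omitted variable against the Protocol's own text**

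| Variable | Reason for not operating (Appendix A) | Linked to death | Collected for NoLAP | In model |
|---|---|---|---|---|
| NELA score | Yes | Yes, potential marker (aim 3) | Yes | No |
| Diagnosis | Yes | Yes, by its label in Appendix A | Yes | No |
| Comorbidity | Yes | Not stated; assumed here | Yes | No |
| Lactate, creatinine | Not listed | Yes, within NoLAP (Background) | Yes | No |
| Frailty | Yes | Yes (Background, aim 3) | Yes | Yes |

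NELA score and diagnosis are supported on both sides, and comorbidity on the decision side. Lactate and creatinine are supported only as prognostic markers.

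**2. The Protocol's own sample size**

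The only calculation given is for the NoLAP proportion: n = 1.96² × 0.32 × 0.68 / 0.0375² = 594, against 590 stated. This reproduces; the half-width at 590 is 3.76%. No figure is given for the mortality model, so none is contradicted here. The formula treats the sample as the denominator of the 32%, whereas the Study Synopsis applies 700 to a cohort that did not undergo laparotomy. Both readings are carried into step 4.

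**3. How large the bias could be (illustration)**

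Assumptions not in the documents: one binary severity factor, independent of age, sex and frailty; prevalence pE in ELAP and pN in NoLAP; odds ratio for death S; no true NoLAP difference (odds ratio 1). From the Protocol: ELAP 90-day mortality 20%.

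Let o be the odds of death without the factor. Solve (1 − pE) × o/(1 + o) + pE × S·o/(1 + S·o) = 0.20 for o. NoLAP mortality is the same expression with pN in place of pE. The spurious odds ratio is the NoLAP odds divided by 0.20/0.80 = 0.25.

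Example with pE = 0.20, pN = 0.60, S = 4: o ≈ 0.173, so risk is 0.148 without the factor and 0.409 with it. NoLAP mortality = 0.4 × 0.148 + 0.6 × 0.409 = 0.305. Odds ratio = (0.305/0.695)/0.25 = 1.75.

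| pE v pN | S = 2 | S = 4 | S = 8 |
|---|---|---|---|
| 20% v 40% | 1.16 | 1.35 | 1.56 |
| 20% v 60% | 1.33 | 1.75 | 2.26 |

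**4. Whether there are enough deaths for more covariates**

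Inputs: NoLAP mortality 67% (one third alive at 30 days, Background; used for 90 days, so probably low) and ELAP mortality 20% at 90 days (Patient numbers and power calculation).

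- 700 is the whole cohort: 224 NoLAP and 476 ELAP. Deaths = 224 × 0.67 + 476 × 0.20 = 150 + 95 = 245.
- 590 followed up: 189 and 401. Deaths = 127 + 80 = 207.
- 700 are all NoLAP: ELAP = 700 × 0.68/0.32 = 1,488. Deaths = 469 + 298 = 767.

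At 10 deaths per parameter, even 207 allows about 20 parameters.

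**The case against.** The strongest reply is that the Protocol makes no causal claim. Aim 4 speaks only of comparing the groups, and the Data analysis section of a difference in mortality. For a descriptive comparison, three basic covariates are a choice rather than an error. NELA score and comorbidities are described elsewhere in that section, aims 3 and 4 compare prognostic markers across groups, and Study Dissemination plans a paper on exactly that. A full SAP is promised before data lock and could add models.

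Much of this stands. A reader might infer that the Protocol presents the contrast as the effect of withholding surgery; it does not say so. But describing markers by group does not adjust the mortality comparison for them. And the covariate set is not left open for the SAP: it is stated, for an analysis called primary.

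A reader might also infer that lactate and creatinine drive the decision. Appendix A lists neither, so the point does not rest on them.

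Two practical objections also stand. The collection list is written for NoLAP patients, and the documents do not list the fields held in NELA and ELLSA, so a covariate could be absent for every ELAP patient. And if some pathologies are almost always NoLAP, adjusting for diagnosis relies on extrapolation.

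**Conclusion.** The point holds as an improvement to the adjustment set. The Protocol fixes a three-covariate model for a primary comparison while naming NELA score, pathology and comorbidity as reasons for the decision that defines the groups. Confounding by indication is likely, and the richer model would reduce it without removing it.

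The size of the bias cannot be computed from the documents. The spurious odds ratio of about 1.2 to 2.3 rests wholly on the assumed prevalences, severity effect and independence from age, sex and frailty. The death counts rest on mixing a 30-day with a 90-day figure, and on which reading of 700 is meant; the conclusion that numbers suffice holds under both readings.

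A reader might infer that the word difference makes an odds ratio the wrong measure here. With 67% and 20% the crude odds ratio is (0.67/0.33)/(0.20/0.80) = 8.1 and the risk ratio 0.67/0.20 = 3.35, so the scales do diverge. But difference is ordinary wording for a group comparison, and 90-day mortality is to be described anyway, so absolute risks will be visible. That is a reporting preference, not an error.

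**What to change.** In the Data analysis section, and carried into the SAP before data lock:

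- Add NELA-predicted risk (logit scale), diagnosis group and comorbidity (Charlson or count) to the multilevel model, using those confirmed as available for ELAP patients in NELA and ELLSA.
- Use lactate and creatinine only in place of the NELA score or in a sensitivity model, because entering them together may count the same information twice.
- Report the age-sex-frailty model beside the fuller one.
- Tabulate group by diagnosis to check overlap before relying on the adjusted estimate.
- State that the contrast is not the causal effect of surgery.

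The change needs no new variables for NoLAP patients. It does need a check of the NELA and ELLSA fields, and of whether diagnosis can be grouped alike in both sources. The costs are some missing values to handle, possible loss of a covariate that is absent for ELAP, and weak information for pathologies that are almost always NoLAP.
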